11.4 CAUSAL RELATIONSHIP

The investigator and sub-investigator should always be alert to adverse events that may be related to the study device or the use of the study device (i.e., the procedure specific to the

initial application of the device). An attempt should be made by either the investigator or the sub-investigator in every case to determine the causality of the event. The following definitions are to be used as guidelines in determining the relationship between the event and the study device and/or use of the device.

Definitely related: If the event is associated with the device and/or the use of the device beyond a reasonable doubt, a causal relationship exists between the adverse event and the device and/or the use of the study device.

Probably related: There is a reasonable possibility of a causal relationship between the adverse event and the device and/or the use of the study device and/or the adverse event cannot be reasonably explained by another cause.

Possibly related: The adverse event has not been determined to be related to the device or the use of the device, but no other cause has been identified and the device and/or the use of the study device cannot be ruled out as a possible cause.

Unlikely to be related: The possibility of a potential causal relationship between adverse event and the device and/or the use of the device could exist, but the adverse event can be reasonably explained by another cause.

Not related: There is no possibility of a causal relationship between the adverse event and the device and/or the use of the study device and/or the adverse event can be attributed to another cause.

If an adverse event is believed to be, probably or possibly related to the study device and/or the use of the device, the event will be considered related to the study device and/or the use of the device.

11.5 ADVERSE EVENT FOLLOW-UP

For every adverse event, appropriate measures should be undertaken to treat and/or monitor the subject until resolution occurs. Obtain and maintain in the subject's files all pertinent medical data relating to the event including the subject's medical records and medical reports and/or judgments from colleagues or outside specialists who assisted in the treatment and follow-up of the subject. The investigator should keep JJSV closely informed as to the outcome of serious and/or device-related adverse events, thereby allowing JJSV to comply with the appropriate regulatory reporting requirements. An Unscheduled Visit form should be completed each time the subject returns to the investigator or other specialist(s) for follow-up of a serious and/or device-related adverse event until resolution of the event and the SAE/ADE form should be updated as necessary (e.g., to document the resolution of the SAE/ADE). Any subject who is exited from the study due to a serious and/or device-related adverse event will be followed until the outcome is determined.

12. PROTOCOL CHANGES/AMENDMENTS

If the investigator desires to modify any procedure and/or the design of the study, he or she must contact and obtain consent from JJSV regarding the proposed changes prior to implementation. Any modifications (including additional data collection) require approval by the

appropriate regulatory agencies as well as approval of the governing IRB(s) prior to implementation.

13. ETHICS REVIEW AND PATIENT WELFARE

13.1 INSTITUTIONAL REVIEW BOARD (IRB)

It is the responsibility of the investigator to obtain prospective approval of the study protocol, protocol amendments or changes, informed consent forms and other relevant documents (e.g., advertisements) from the IRB. All correspondence with the IRB should be retained at the site. Copies of IRB submissions and approvals should be forwarded to JJSV.

The investigator is responsible for notifying the IRB of reportable adverse events as well as any other circumstance in which additional procedures outside the protocol were conducted to eliminate apparent hazards to subjects.

13.2 INFORMED CONSENT

The current version of the IRB-approved study informed consent must be signed by each study subject prior to any study-specific examinations being performed. The IRB-approved informed consent is to be signed and dated by the subject as well as by the person who conducted the informed consent discussion. The signed informed consent will be maintained by the investigator as a permanent part of the subject's medical records. A copy of the signed and dated form is to be provided to the subject. The investigator will provide JJSV written acknowledgement on the preoperative case report form that a signed agreement of informed consent has been obtained and is in the investigator's possession for each subject. The site will document in the source documents that informed consent was obtained prior to participation in the study for each subject enrolled.

NOTE 1: *The informed consent process also includes obtaining the subject's signature on an Authorization for Use/Disclosure of Health Information for Research Form.*

NOTE 2: *The sponsor will secure appropriate insurance for study subjects prior to study start.*

14. DOCUMENTATION

14.1 SOURCE DOCUMENTS

Source documents must be kept for all study subjects. Source documents may include a subject's medical records, hospital charts, clinic charts, the investigator's subject study files, as well as results of any diagnostic tests or procedures such as topographies or laboratory tests with photographs or instrument printouts.

Each site is expected to adhere to the clinic's own standard documentation requirements for medical charts/clinic notes. However, for the purposes of this clinical study, the medical charts/clinic notes must also include, at a minimum, the following data that will be considered source data and will be reviewed by JJSV:

- Subject's name and study identification number
- Subject's contact information
- Study protocol number and the Sponsor name (JJSV)
- A statement that informed consent was obtained prior to participation in the study (including the date)
- Dates of all subject visits and surgeries throughout the duration of the study
- Implant serial number identification
- Concomitant medications
- Uncorrected distance visual acuity
- Manifest refraction and best corrected distance visual acuity
- Occurrence and status of any operative complications, postoperative medical or lens findings, and adverse events
- Occurrence and status of any subject complaints, e.g., ocular/visual symptoms
- The date the subject exited the study, and a notation as to whether the subject completed the study or reason for early exit.

14.2 SUBJECT CONFIDENTIALITY

Eyes will be assigned a site/ID number to maintain confidentiality. Subject names may possibly be disclosed to JJSV or regulatory agencies during inspection of medical records related to the study, but reasonable precautions will be taken to maintain confidentiality of personal information to the extent permitted by applicable laws and regulations.

14.3 CASE REPORT FORM COMPLETION

This study will use an electronic data capture system (EDC). All study staff responsible for entering data into the system must complete certification prior to using the system. The investigator is responsible for ensuring that data are properly recorded on each subject's case report form and related documents. Prior to database closure, the investigator will verify completeness and accuracy of all data collected and submitted to JJSV.

14.4 STUDY SUMMARY

A final investigator's summary will be provided to JJSV and the reviewing IRB within 3 months after termination or the completion of the study or the investigator's part of the investigation, as directed by JJSV.

15. MONITORING

JJSV will perform three types of monitoring to ensure compliance with regulations: data monitoring, administrative monitoring, and safety monitoring.

15.1 DATA MONITORING

In order to ensure a well-controlled clinical trial, JJSV will follow specific data monitoring procedures, routinely generate reports and periodically review safety and effectiveness data. To avoid bias, any analyses generated prior to site closures will not be disseminated to any of the investigative sites.

An EDC system will be used to transmit case report forms from the investigative site to JJSV. Requests for data clarification will be handled through this same system.

To minimize data omissions and inconsistencies on clinical reports and to ensure that data are accurately transcribed to computer data files, JJSV will follow internal data processing procedures that include automated and manual quality control checks to identify any data discrepancies. Any such items will be resolved and documented as needed on the case report forms at the investigative site and in the data management system at JJSV.

Prevention of Missing Data

Methods used to safeguard against missing data that can have deleterious effects on the study integrity and reliability of its outcomes will include training study staff with web-based and/or on-site programs. In addition, subjects will be encouraged at the time of informed consent to avoid missing study visits, as missing data may affect the study reliability and diminish the scientific value of their contribution to the study.

15.2 ADMINISTRATIVE MONITORING

Administrative monitoring procedures will ensure that subjects, and forms can be traced and will allow monitoring of investigator progress and compliance. Accountability and traceability of study devices will be monitored by trained JJSV personnel.

Site Monitoring Plan

Prior to performing any study implants, the requirements of the study and reporting mechanisms will be explained to each investigator during the web-based or on-site training. When necessary, a pre-study site qualification visit may be performed to assess the adequacy of the site to perform the study for sites that have not previously worked with JJSV or have undergone significant changes or have not been visited in the past year or have not had a Site Qualification Visit in the last 24 months. A study initiation visit will be conducted (either in-person or via a web-based meeting) for all sites prior to the first implant.

Throughout the duration of the study, site visits to monitor compliance to this protocol will be made at each site. During a routine site monitoring visit, JJSV will review informed consent documents and subject eligibility, and the data on study case report forms will be verified against subject charts and other source documents to ensure complete and accurate reporting. The subject files will also be reviewed to assure that all adverse events and any issues encountered with JJSV products have been reported in a timely fashion.

JJSV will also review source documents to verify that all required items have been documented in the subject medical charts. Refer to Section 14.1, Source Documents, for a list of items that are required for source documentation. Additionally, study logs will be checked to ensure compliance with study procedures.

Training on study-specific procedures may also be conducted during monitoring visits.

Upon study completion, a final close-out site visit to each site will be made to monitor the last of the subject data records and finalize any outstanding study issues.

A separate Study Monitoring Plan will be established prior to study start that will define the type and frequency of monitoring visits and frequency of record monitoring.

15.3 MEDICAL OVERSIGHT

The medical monitor will be available throughout the clinical trial to review study results and to answer any questions from investigators. The medical monitor will review and assess any reports of serious and/or device related adverse events, as well as, device deficiencies that could have led to a serious adverse event and discuss them with the reporting investigator(s) as necessary. The medical monitor, as well as, any other qualified personnel designated by JJSV, shall also review study reports.

16. PUBLICATIONS

Refer to the Clinical Trial Agreement for information regarding JJSV publication policies.

17. RISK ANALYSIS

POTENTIAL RISKS AND RISK MANAGEMENT

RISKS OF THE TECNIS TORIC II INTRAOCULAR LENS

The acrylic 1-piece IOL TECNIS Toric II is designed to have improved rotational stability relative to the currently marketed TECNIS Toric 1-piece IOL (ZCT Series). The lenses are made from the same SENSAR soft acrylic material that is used in marketed TECNIS 1-piece lenses. Its aspheric anterior surface is intended to compensate for corneal spherical aberration.

The risk documentation for the currently marketed TECNIS 1-piece lenses, ZCB00 and ZCT Series, is applicable. For ZCB00 and ZCT lenses, current risk documentation concludes that all risks are identified as low or medium and deemed acceptable.

An additional risk assessment for the TECNIS Toric II was conducted to analyze potential hazardous situations resulting from the design differences compared to the ZCB00 and ZCT designs. With the implementation of a Risk Control Plan under this risk assessment, no additional safety issues have been identified for the study products for their intended use in the proposed clinical investigation.

GENERAL RISKS OF CATARACT SURGERY AND IOL IMPLANTATION

There are risks and complications associated with cataract surgery and IOL implantation in general. These can include worsening of vision, hemorrhage, loss of corneal clarity, inflammation, infections, retinal detachment, pupil changes, glaucoma, etc. Complications can result in poor vision, loss of vision or loss of the eye.

RISK MANAGEMENT

Subjects will be closely monitored throughout the trial duration. The occurrence of adverse events and complaints will be assessed at each study visit and reported to JJSV according to Section 11.0, Adverse Events and Product Complaints. Additionally, JJSV will monitor incoming

data following the procedures outlined in Section 15.0, Monitoring. The Medical Monitor will ensure subjects are not exposed to additional risks by monitoring serious adverse events, device-related adverse events, and device-deficiencies that could have led to serious adverse events (Section 15.3, Safety Monitoring).

POTENTIAL BENEFITS

The general clinical performance of the TECNIS Toric II is expected to be similar to the TECNIS Toric ZCT lens series. The primary benefit from implantation of the TECNIS Toric II is the correction of astigmatism following removal of the natural crystalline lens due to cataract.

CONCLUSION

The hazards/risks associated with the TECNIS Toric II are acceptable and within those of JJSV's currently marketed IOLs. The potential clinical benefits of the TECNIS Toric II IOL outweigh the residual risks when the devices are used as intended.

18. RECORDS RETENTION

All study-related correspondence, subject records, consent forms, Authorization for Use/Disclosure of Health Information Forms or similar medical treatment privacy law documentation, records of the distribution and use of all study products, and original case report forms should be maintained by the investigator.

The investigator must maintain and have access to the following essential documents until notified by the Sponsor.

NOTE: This may be for a minimum of 15 years after completion of the study. JJSV requires notification if the investigator wishes to relinquish ownership of the data so that mutually-agreed-upon arrangements can be made for transfer of ownership to a suitably-qualified, responsible person.

- All case report forms within the EDC system
- All adverse event information (SAE/ADE detailed pages, follow-up letters, etc.)
- Study supply records/inventory
- IRB and regulatory approval documentation
- Study correspondence
- Study agreements
- Site visit documentation
- Protocol(s) and the reason for any deviations from the protocol
- Subject log(s)
- Completed subject informed consent forms and medical privacy forms (e.g., Authorization for Use/Disclosure of Health information)
- Subject medical chart/clinic notes

19. TERMINATION OF THE INVESTIGATION

JJSV can suspend or terminate the clinical investigation at any time for reasons it determines appropriate. Additionally, the investigator, or JJSV, may stop a subject's participation at any time. However, no suspension of the study would be made to disadvantage the study subjects. Following suspension of the study for any reason, all study subjects who have already received treatment would continue to be followed through completion of the study visit schedule.

20. STATISTICAL METHODS

This section highlights the analyses to be performed for key study endpoints. The 3-month postoperative visit is the critical analysis time point for the primary endpoint and for other data from the SSQ questionnaire, the SEQ questionnaire and for refraction and visual acuity endpoints. The operative visit is the key timepoint for evaluation of data from the SHQ questionnaire. The one-week visit is the key timepoint for the SSQ question on rotational stability.

Descriptive statistics will typically include mean, standard deviation, median, minimum, maximum for continuous data with frequency and proportion reported for categorical data.

20.1 ANALYSIS POPULATION

For the primary endpoint, the primary analysis population will be all eyes implanted with a toric IOL (model ZCU150 through ZCU600) and with available data at the 3-month visit. For other endpoints, all eyes implanted with a toric IOL model ZCU150 to ZCU600 and with available data at the key timepoint for that endpoint will be used. In addition, data for the primary endpoint will also be evaluated by IOL model for lower-cylinder IOLs (ZCU150), medium-cylinder IOLs (ZCU225 to ZCU375) and for extended higher-cylinder IOLs (ZCU450, ZCU525 and ZCU600). For the surgeon preference questionnaire (SPQ) and the surgeon experience questionnaire (SEQ), the analysis population will be surgeons responding to these questionnaires.

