10.8 EXIT OF SUBJECTS

An Exit Case Report Form will be completed for all subjects, either when they complete the study or if they exit early.

It is the responsibility of the investigator to provide complete follow-up data to JJSV for each subject, and every attempt should be made to gather that complete follow-up data for all subjects enrolled as missing data can have a negative effect on the study results. Patients who would be traveling, relocating or otherwise unavailable for postoperative follow-up visits should not be chosen for this clinical study.

Subjects will be discontinued from the study if the study lens is removed and the fellow eye does not have a study IOL or if the subject dies. Subjects will be considered "lost-to-follow-up" from the study only if irretrievably lost for unavoidable reasons such as: subject moved/unable to locate, subject uncooperative/refuses further study participation, subject ill/unable to travel.

A subject will be considered a screen failure if he/she does not meet the enrollment criteria. A subject will also be considered a screen failure if he/she does not undergo surgery or receive a study lens for various reasons including: the planned implant being aborted due to surgical complications, the subject withdrawing consent prior to treatment or the subject died prior to

treatment. If a subject receives at least one study lens, he/she is to be followed according to the protocol.

If a subject is exited early from the study, the investigator will submit an Exit Case Report Form to JJSV indicating the reason for study exit. In the event of a lens removal or other serious adverse event, the subject may be exited from the study; however, efforts must be made by the investigator to follow the subject until resolution of the adverse event.

All study subjects are to be instructed to undergo regular eye examinations at least yearly and to return to their doctor if any eye complications are experienced in the interim.

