- Visual symptoms requiring secondary surgical intervention (e.g., lens removal)
- Tilt, decentration, IOL rotation requiring secondary surgical intervention (e.g., repositioning)
- Residual refractive error resulting in a secondary surgical intervention
- Retained lens material resulting in secondary surgical intervention

NOTE 1: *Wound burps during the first week postoperatively, suture removal, planned blepharoplasty and Nd:YAG capsulotomy (for PCO) are not considered adverse events for this study.*

NOTE 2: *Corneal edema, and chronic anterior uveitis/iritis will be considered serious if corneal edema resulting in BCDVA of 20/40 or worse at 1 month or later; and Grade 1+ uveitis/iritis persists for greater than 3 months after surgery). Raised IOP requiring treatment (Elevation of IOP \geq 10 mmHg above baseline to a minimum of 25 mmHg) will be considered serious if present at the last study visit.*

Unanticipated Adverse Device Effect (UADE)/Unanticipated Serious Adverse Device Effect (USADE)

Any USADE (ISO 14155) is defined as any serious adverse effect on health or safety or any life-threatening problem or death caused by, or associated with, a device, if that effect, problem, or death was not previously identified in nature, severity, or degree of incidence in the investigational plan (i.e., this protocol), application (including a supplementary plan or application), or risk assessment, or any other unanticipated serious problem associated with a device that relates to the rights, safety, or welfare of subjects.

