20.2 PRIMARY ENDPOINT

The primary endpoint for this study is the response to a single-item evaluating the surgeon's rating of overall level of satisfaction with the clinical outcome for each eye from the SSQ. Surgeon satisfaction is defined as having a score of 4 (satisfied) or 5 (very satisfied). The frequency and proportion of eyes with a rating of 4 or 5 and the 95% confidence interval for this proportion will be reported. In addition, the frequency and proportion with each response will be tabulated for this item.

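### Eyes explanted before 3 months can leave the primary satisfaction proportion unrated, and no planned analysis shows how far that could raise the figure

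*Combined protocol and SAP*

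**What the plan says.** - **Population.** Section 20.1 defines the primary population as "all eyes implanted with a toric IOL (model ZCU150 through ZCU600) and with available data at the 3-month visit".
- **Endpoint.** Section 20.2: "Surgeon satisfaction is defined as having a score of 4 (satisfied) or 5 (very satisfied"). The planned output is one proportion with its interval: "The frequency and proportion of eyes with a rating of 4 or 5 and the 95% confidence interval for this proportion will be reported". No success threshold or test is stated.
- **Timing of the rating.** Section 10.7, Appendix A and Attachment C place the overall satisfaction item at the 3-month visit only. The 1-week visit collects only the rotational stability item. The section 10.9 list of data for unscheduled visits does not include the questionnaire, and no rating at exit or at lens removal is described.
- **Exit after lens removal.** Section 10.8: "Subjects will be discontinued from the study if the study lens is removed and the fellow eye does not have a study IOL". Later in the same section: "In the event of a lens removal or other serious adverse event, the subject may be exited from the study", with follow-up of the adverse event until it resolves.
- **Missing ratings.** Section 15.1 covers prevention of missing data. Sections 20 to 20.5 contain no imputation, no rule for implanted eyes without a rating, and no sensitivity analysis.
- **Where removals would appear.** They would show in the adverse event and secondary intervention tables (6.2, 20.3), the accountability data (20.3) and the Exit Case Report Form (10.8).

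**The concern.** The clinical hypothesis in section 3 is about eyes that were implanted, not eyes that still held the lens at 3 months. In a subject without a study lens in the fellow eye, the protocol ties an unfavourable course (the lens came out) to a missing primary value. This differs from ordinary loss to follow-up, where the reason for absence need not concern the lens.

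Leaving such eyes out is neutral only if they would have been rated like the rest. The documents do not say how they would be rated. A lower rating is plausible, since section 11.1 lists among the anticipated serious events "Visual symptoms requiring secondary surgical intervention (e.g., lens removal"). If ratings would be lower, the headline proportion is too high. Its confidence interval does not show this, because it reflects sampling error and not selection.

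**Working it through.** **Inputs.** From section 20.4: at least 1000 eyes, an expected proportion of 95%, and a stated precision of 1.4%. The number of explanted, unrated eyes (e) and the share of them that would have been rated 4 or 5 (s) are not in the documents and are assumptions here.

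**Step 1: the plan's own figure.** Half-width = 1.96 × √(0.95 × 0.05 / 1000) = 0.0135, or 1.35 points. This agrees with the stated 1.4%. It treats eyes as independent.

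**Step 2: effect on the proportion.** With n rated eyes, 95% of them satisfied, the proportion including the explanted eyes is

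p = (0.95n + s·e) / (n + e).

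For n = 1000:

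| e | s | Calculation | Proportion | Shift from 95.0% (points) |
|---|---|---|---|---|
| 5 | 0 | 950/1005 | 94.5% | 0.47 |
| 10 | 0 | 950/1010 | 94.1% | 0.94 |
| 15 | 0 | 950/1015 | 93.6% | 1.40 |
| 10 | 0.5 | 955/1010 | 94.6% | 0.45 |
| any | 0.95 | – | 95.0% | 0 |

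**Step 3: when the shift matches the interval.** If f is the share of implanted eyes that are explanted and unrated, the upward bias is f × (0.95 − s). It is positive whenever s is below 0.95. It equals the half-width at f = 1.35/95 = 1.42% when s = 0, and at f = 1.35/45 = 3.0% when s = 0.5. In counts with s = 0, the shift first exceeds the half-width at 15 eyes per 1000 rated (1.40 against 1.35 points). At 14 eyes it is 95.00 − 950/1014 = 95.00 − 93.69 = 1.31 points.

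**Step 4: cylinder groups.** Section 20.1 also reports the endpoint in three cylinder groups, where each eye weighs more. In a group of 100 rated eyes at 95% (an assumed size), one such eye gives 95/101 = 94.06%, a shift of 0.94 points.

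**Step 5: is counting them as failures closer to the truth?** Leaving the eyes out overstates the proportion by e(0.95 − s)/(n + e). Counting all of them as not satisfied understates it by e·s/(n + e). The second error is smaller only if s < 0.95 − s, that is, s below 0.475. At s = 0.5 and e = 10 the two errors are +0.45 and −0.50 points. The count-as-failure figure is therefore a lower bound for these eyes and not a better estimate in every case.

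**The case against.** The strongest case against acting is that materiality is not shown. The bias needs three things: lens removals before 3 months, no rating for those eyes, and a lower rating had one been given. The documents quantify none of them. The result is descriptive, and a reader can already find removals in the safety and accountability tables. All of this stands as a limit on weight. It does not remove the gap: those tables show that eyes were removed, but leave the headline proportion and its interval as they are.

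Several stronger readings are tempting, and the documents do not support them:

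- **That every explanted eye is lost.** The mandatory discontinuation applies only when the fellow eye has no study lens. A bilaterally implanted subject may stay in the study and the eye may still be rated. Section 10.8 also asks sites to make every effort to obtain complete follow-up. The more bilateral the sample, the fewer eyes the mandatory rule reaches.
- **That section 10.8 holds three competing explant rules.** The sentence "If a subject receives at least one study lens, he/she is to be followed according to the protocol" closes the paragraph that defines screen failures. In context it separates implanted from never-implanted subjects. Only the mandatory and the permissive statements on lens removal overlap.
- **That section 11.1 shows explanted eyes would be rated poorly.** The item "Residual refractive error resulting in a secondary surgical intervention" does not mention removal, and for rotation the list gives repositioning as its example. A repositioned eye keeps its lens and can be rated. The list makes a lower rating plausible and does not establish it.
- **That the primary denominator should be replaced.** The endpoint is a surgeon's rating. Assigning a failure where no rating exists changes that endpoint and, by Step 5, can err about as far in the other direction.

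**Conclusion.** The point holds as a limited, conditional one. As written, the plan drops from the primary proportion any eye that is explanted before 3 months and unrated, and it has no analysis that shows the effect. The bias is upward if such eyes would be rated 4 or 5 less often than retained eyes, and nil if they would be rated alike. Its size is unknown. With 950 of 1000 rated eyes satisfied and none of the explanted eyes satisfied, 5 to 15 such eyes would lower 95.0% to between 94.5% and 93.6%. Fewer than 15 would keep the shift within the 1.35-point half-width.

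A reader might infer that the study's conclusion is at risk. The documents do not support that: no threshold or test is set, so what is affected is the accuracy of one reported percentage and, with more weight per eye, its cylinder-group versions. This is a cheap improvement to make before the data are seen, not a fault that invalidates the primary analysis.

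**What to change.** 1. Keep the available-data proportion in sections 20.1 and 20.2 as it is.
2. Pre-specify in both sections an analysis reported beside it, overall and for the three cylinder groups. Eyes explanted before the 3-month questionnaire and left unrated count as not satisfied. Every observed rating stands as recorded, including ratings of exchanged or repositioned eyes.
3. Add a worst case over all implanted eyes in which every unrated eye, for whatever reason, counts as not satisfied.
4. Report the number of unrated implanted eyes by reason.
5. Reconcile the two overlapping statements in section 10.8 on exit after lens removal. This review does not say which is right.

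**Cost.** Some analysis wording and a few table rows. No new data are needed, because adverse events are already reported under section 11.3 and exit reasons are on the Exit Case Report Form. The added figures will be slightly lower than the headline. They understate satisfaction if some of these eyes would have been rated 4 or 5, so they should be labelled as bounds.
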